Hypothesis #1B: *Whole blood resuscitation will be associated with a lower incidence of 12 hour and 24 hour mortality, a lower incidence of death from exsanguination, incidence of MOF, nosocomial infection, improved transfusion ratios, lower overall blood transfusion requirements and shorter time to hemostasis as compared to those resuscitated with component therapy.*

Hypothesis #1C: *Whole blood resuscitation will be associated with an improved Glasgow Outcome Score-Extended at 6 months post injury as compared to those resuscitated with component therapy in patients with traumatic brain injury.*

Hypothesis #2A: *A nadir prehospital and acute phase resuscitation systolic blood pressure greater than or equal to 120 mmHg will be associated with improved traumatic brain injury outcomes at discharge and at 6 months.*

Linking Investigations in Trauma and Emergency Services

Task Order 2: Shock, Whole blood and Assessment of TBI (SWAT)

Hypothesis #2B: *The magnitude of the dose depth curve of systolic blood pressure during the prehospital and acute phase resuscitation will be associated with neurological outcome differences at discharge and at 6 months following traumatic brain injury.*

Research Design and Methods

Study Design: The LITES Network will perform a multicenter, prospective, observational cohort study over a 4 year period to determine the impact of whole blood resuscitation in trauma patients with hemorrhagic shock at risk of large volume resuscitation with and without TBI. Early whole blood resuscitation will be compared to standard component resuscitation. The study will also further characterize blood pressure and resuscitation endpoints in poly-trauma patients with traumatic brain injury. Six trauma sites with appropriate characteristics will be selected from network sites across the country. (Figure 2)

Figure 2

Study Setting: The study will be performed utilizing busy level I trauma centers from within the LITES Network located across the country, at sites where either whole blood has currently been incorporated into standard of care or where component blood transfusion is being utilized for patients in hemorrhagic shock at risk for large volume resuscitation. Due to the paucity of trauma centers who are currently utilizing whole blood for trauma patients as standard of care, the potential to incorporate additional sites may be required over time.

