Finally, for time to event analyses (e.g., time to hemostasis), a bivariate hierarchical Cox proportional hazards regression model will be generated to compare the time to event between those receiving and those not receiving whole blood. Again, the hierarchical model will be used to control for within-institution clustering. In a second step, to determine the independent effect of whole blood after controlling for potential confounding effects, the propensity score will be added to the model.

Hypothesis#1C: A two-sided z-test for correlated proportions will be used to compare the distribution of GOS-E proportions between those receiving and not receiving whole blood. This

Linking Investigations in Trauma and Emergency Services

Task Order 2: Shock, Whole blood and Assessment of TBI (SWAT)

test will be used to control for the within-institution clustering. A hierarchical polytomous logistics regression model will then be used to assess the independent impact of whole blood after controlling for the clustering effect and the potential confounding effects of baseline characteristics. The model will include main effects for whole blood usage and propensity for receiving whole blood.

AIM#2: The analyses for the second aim will be restricted to the subset of participants who will be characterized as having a traumatic brain injury.

Hypothesis#2A: The analysis will begin by comparing the baseline characteristics of those with a prehospital and acute phase resuscitation systolic blood pressure greater than or equal to 120 mmHg to those who do not. For discrete variables, proportions will be generated and a chi-squared test will be used to test for differences between the proportions. For continuous characteristics, means (medians) and standard deviations (interquartile ranges) will be calculated and t-test (Wilcoxon) test will be used to compare the means (distributions) among those who receive and do not receive whole blood.

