A two-sided z-test for correlated proportions will be used to compare the distribution proportions of GOS-E at 6-months between those with a prehospital and acute phase resuscitation systolic blood pressure greater than or equal to 120 mmHg to those who do not. A hierarchical polytomous logistics regression model will be used to control for the within-institution clustering. The model will be used to assess the independent impact of whole blood after controlling for the clustering effect and the potential confounding effects of baseline characteristics. As was done in Aim#1A, the propensity for a prehospital and acute phase resuscitation systolic blood pressure greater than or equal to 120 mmHg will be generated using a boosted logistic regression model which will include all baseline characteristics, including site and whole blood usage. The same analytic approach will be used to measure outcomes at discharge except a hierarchical logistic regression model will be used.

Hypothesis#2B: The area under the curve of systolic blood pressure during the prehospital and acute phase resuscitation will be generated for each study participant. The analysis will begin by comparing the baseline characteristics with the area under the curve. For discrete variables, bivariate linear regression models will be generated (area under the curve as the dependent variable and the discrete baseline characteristic as the independent variable). For continuous characteristics, the correlation will be assessed.

Hierarchical models will be used to adjust for within-institution clustering. Hierarchical bivariate linear regression models will be used to assess the association of baseline characteristics associated with area under the curve. A stratified propensity analysis will be used to estimate the association of area under the curve with GOS-E at six months. A hierarchical linear regression

Linking Investigations in Trauma and Emergency Services

Task Order 2: Shock, Whole blood and Assessment of TBI (SWAT)

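### Aim 2: the 2A adjusted model is written for whole blood, not SBP ≥120 mmHg; the 2A effect size of 0.28 fits about 80% power, not the stated 90%; and the 2B pressure area is tied to early death

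*Combined protocol and SAP*

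**What the plan says.** **2A, exposure.** The hypothesis under Objectives/Specific Aims/Hypothesis is that "A nadir prehospital and acute phase resuscitation systolic blood pressure greater than or equal to 120 mmHg will be associated with" better TBI outcomes at discharge and 6 months. Under Analyses, Hypothesis#2A:
- The description starts by "comparing the baseline characteristics of those with a prehospital and acute phase resuscitation systolic blood pressure greater than or equal to 120 mmHg" with the remaining patients, but the tests for continuous characteristics are said to "compare the means (distributions) among those who receive and do not receive whole blood".
- The unadjusted test is by SBP group: "A two-sided z-test for correlated proportions will be used to compare the distribution proportions of GOS-E at 6-months".
- The adjusted model is a hierarchical polytomous logistic regression, of which the plan says: "The model will be used to assess the independent impact of whole blood after controlling for the clustering effect and the potential confounding effects".
- Next, the plan says "the propensity for a prehospital and acute phase resuscitation systolic blood pressure greater than or equal to 120 mmHg will be generated" by boosted logistic regression, with site and whole blood use among the covariates.

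The word nadir does not appear in this analysis text.

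**2A, power.** The Power Analysis section gives a detectable effect size of 0.28 for a nonparametric analysis of variance of GOS-E between two groups. The settings are two-sided 0.05, 90% power and 417 TBI patients (35% of 1,190). It gives neither the scale of 0.28 nor the split between the SBP groups.

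**2B.** The hypothesis refers to "The magnitude of the dose depth curve of systolic blood pressure during the prehospital and acute phase resuscitation". The analysis says: "The area under the curve of systolic blood pressure during the prehospital and acute phase resuscitation will be generated for each study participant". A linear model on baseline characteristics yields five propensity strata, and GOS-E at 6 months is then regressed on the area by polytomous models. The acute phase is not bounded in time for this purpose, and there is no rule for records that end at death.

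**The concern.** For 2A, the adjusted estimate is the one that would be reported, and taken literally it is an estimate for whole blood. The powered test also differs from the planned ones, and the stated sensitivity appears to belong to a lower power.

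For 2B, the exposure is a sum over time. At a constant 110 mmHg, a record ending at 60 minutes has area 110 × 60 = 6,600 mmHg·min, and one ending at 240 minutes has 110 × 240 = 26,400. If the short record ended in death, the patient also holds the worst GOS-E category. Small areas then go with bad outcomes even if pressure plays no part. Strata built from baseline characteristics are not designed to remove a difference that arises after baseline.

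Hypotheses 2A and 2B make up the whole of Aim 2.

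**Working it through.** **2A wording.** Hypothesis, opening baseline sentence, z-test and propensity score: SBP ≥120. Adjusted model and continuous baseline comparisons: whole blood. The corresponding models for 1A, for the continuous outcomes in 1B and for 1C each say that the exposure and its propensity score enter as main effects. 2A has no such sentence.

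**2A power.** Inputs from the Power Analysis: effect 0.28, N = 417 (0.35 × 1,190 = 416.5), two-sided 0.05, 90% power. Assumptions: 0.28 is a standardised difference d; the split is even (p = 0.5, the most favourable); efficiency e = 1, or 0.955 for a Wilcoxon-type test with normal data.

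Power = Φ(d√(N·e·p(1−p)) − 1.960).
- e = 1: √(417 × 0.25) = 10.210; 0.28 × 10.210 − 1.960 = 0.899; power 81.6%.
- e = 0.955: √(417 × 0.955 × 0.25) = 9.978; 0.28 × 9.978 − 1.960 = 0.834; power 79.8%.

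Detectable d = (1.960 + z)/√(N·e·p(1−p)).
- 90% (z = 1.282): 3.242/10.210 = 0.317; 3.242/9.978 = 0.325.
- 80% (z = 0.842): 2.802/10.210 = 0.274; 2.802/9.978 = 0.281, which matches the printed 0.28.

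Total N for 0.28 at 90% = 4 × 3.242²/0.28² = 536, or 561 after dividing by 0.955; in equal groups, 538 and 562.

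Other readings also miss 90%. As an ANOVA f, the noncentrality is 417 × 0.28² = 32.7 and power exceeds 99.9%. One-sided 0.05 gives 87-89%, but the plan says two-sided. Unequal splits lower the power.

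| TBI patients | SBP split | Power for 0.28 | Detectable at 90% |
|---|---|---|---|
| 417 | even | 80-82% | 0.32-0.33 |
| 417 | 20/80 (assumed) | 61-63% | 0.40-0.41 |
| 312 (35% of the 892 consented) | even | 68-70% | 0.37-0.38 |
| 312 | 20/80 (assumed) | not run | 0.46-0.47 |

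The 2B precision figure is sound: 2·tanh(1.96/√414) = 0.192 at zero correlation, against the stated 0.19.

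**2B.** Null simulation, with every input assumed: N = 312; SBP mean 110, SD 18, independent of GOS-E; median prehospital time 45 minutes; early deaths uniform over 60-240 minutes with GOS-E 1; other patients spread evenly over categories 2-8, with 0% or 20% later deaths; Spearman test of area against GOS-E. The 11.1% column borrows the whole-cohort control rate from the Power Analysis; the early-death rate in TBI patients is not given. False-positive rates, nominal 5%:

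| Analysis | 2% early deaths | 5% | 11.1% |
|---|---|---|---|
| Area, fixed 4 h window cut only at death | 9-13% | 30-46% | 83-96% |
| Area, record ends at hemostasis (60-240 min) or death | 5-6% | 5-10% | 4-31% |
| Area among patients alive at window end | 4-6% | 4-6% | 4-6% |
| SBP per unit time, no trend | 4-6% | 4-6% | 4-6% |
| SBP per unit time, rising 20 mmHg over 4 h | 5% | 7% | 8% |
| SBP per unit time, rising 40 mmHg over 4 h | 5% | 8% | 15% |

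Under the two rising-pressure settings the landmark analysis stayed at 5-6%. Other assumed hemostasis times (30-120 or 120-240 minutes) widen the second row to 4-43% at 5% deaths and 5-94% at 11.1%. The sign reverses when survivors' records end sooner than those of dying patients.

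**The case against.** **The 2A wording is an evident carry-over.** The heading, z-test and propensity score point to SBP ≥120, whole blood is listed as a covariate of that score, and the score is introduced by reference to Aim 1A. The missing nadir can be read in from the hypothesis. This stands. A reader might infer that the trial will analyse the wrong variable; the surrounding text does not support that. What remains is that the sentence is wrong as written and the model terms are never stated.

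**The power gap is small and conditional.** It is about 0.04 of a standard deviation, on a secondary hypothesis for which the plan already asks for caution, and the scale is the reader's assumption. This also stands, but no scale or split tried gives 90% at the stated settings. The 312 figures come from a separate mismatch in the plan's sample sizes and the 20/80 split is assumed; both show a range only.

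**The 2B artefact is separable in the planned model.** A reader might infer that the plan offers no way to tell record length from blood pressure. That is too strong. Fitted as nominal, the multinomial model confines the artefact to contrasts against death. In a check with a fixed 4 h window and 5% or 11.1% early deaths, the joint test among categories 2-8 rejected in only 1-4% of runs. The overall test still rejected in 37-100%, and the plan does not say which contrast it will report.

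**The high 2B percentages are not an estimate for this study.** They need a fixed 4 h window, which the plan nowhere sets for the SBP area, and a borrowed death rate; ED deaths are excluded. The nearest limit in the text (4 hours, hemostasis or death, in Screening/Outcome Data and Sample Collection) governs resuscitation monitoring and gives much smaller figures at low death rates. Table 1 schedules vitals to 24 hours. The Spearman test is also not the planned model. All of this stands. The lack of a stated window would, on its own, be only missing detail.

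**Conclusion.** The point holds in three limited parts, and the plan should be changed.

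- **2A text.** The adjusted model and the continuous baseline comparisons name whole blood where the hypothesis requires nadir SBP ≥120. The intent is recoverable, so this is a correction of text.
- **2A power.** The stated 0.28 at 90% does not reproduce. As a standardised difference on an even split of 417, it corresponds to about 80% power, and 90% requires 0.32-0.33. This rests on the assumed scale and split.
- **2B.** The raw area depends on record length, and death determines both the end of the record and the worst outcome category. The mechanism follows from the definitions. Its size does not: it ranges from negligible to large with the window and the early-death rate, and even its direction can change. The documents do not support any single inflated error rate for 2B.

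**What to change.** **2A model.** Name nadir SBP ≥120 mmHg, as in the hypothesis, and its propensity score as the terms in the adjusted GOS-E model. Use the same grouping for every 2A baseline comparison.

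**2A power.** State the scale and the test behind the effect size, and align that test with the planned analysis. Then restate either the effect (about 0.32-0.33 at 90%, N = 417, even split) or the power (about 80% for 0.28). Show the larger detectable effect that follows if the SBP groups are uneven or the TBI sample is 35% of 892.

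**2B.** Set one fixed acute-phase window and a rule for records that end at death. Analyse SBP area, or depth below a prespecified threshold, per unit of observed time. Add a landmark analysis among patients alive at the end of the window, with cumulative area in those patients as supporting. State which contrasts of the multinomial model will be reported.

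**Cost.** This is analysis-plan wording and slightly more analysis. Serial vitals are already collected, but their times must be kept. The stated 2A sensitivity becomes less favourable. The per-time measure loses the duration part of dose, which is why cumulative area is kept, and it is not fully protected if SBP trends over the window (up to 15% false positives in the check above). The landmark result applies only to patients who survive the window.

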Death from Exsanguination/Hemorrhage: Those patients who succumb on the operating table, IR suite or ICU due to uncontrolled coagulopathy or hemorrhage in the first 4 hours from arrival will have their mortality classified as exsanguination/hemorrhage. This will be determined by the individual trauma surgeon at the time of the event.

Acute Hemolytic Transfusion Reaction: We will utilize and characterize acute hemolytic transfusion reactions as defined by the CDC/National Healthcare Safety Network (NHSN) Hemovigilance Surveillance definition (www.cdc.gov/nhsn).

Linking Investigations in Trauma and Emergency Services

Task Order 2: Shock, Whole blood and Assessment of TBI (SWAT)

Galveston Orientation and Amnesia Test (GOAT): For TBI subjects, we will obtain the GOAT score at the time of discharge and the calculated score per standard methods.⁴⁸ (Figure 4) GOAT is a 10-item questionnaire used to quickly assess post-traumatic amnesia following head injury. The GOAT is read orally to the patient and may be easily administered at the bedside. The total score accounts for orientation of person, place, and time, and recollection of events pre and post-injury. Cutoff scores are available to identify abnormal, borderline, and normal orientation and it will additionally determine if a subject is able to provide continuing participation consent if consented by proxy.

Extended Glasgow Outcome Scale (6 months-GOSE): For TBI subjects, the GOSE score will be obtained at 6 months +/- 1month by hone survey or direct patient contact, whichever is feasible. For those TBI subjects who were unable to consent at discharge, the GOAT will be administered to assess their ability to provide direct consent, prior to the administration of the GOSE. When the assessment is done by phone, the verbal consent of participants who have regained the ability to consent, will be obtained to allow the GOSE to be completed. The score is able to characterize 6 month functional status into 8 well defined categories as shown in (Figure 5).

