ED Data: Arrival time, serial vitals (GCS, blood pressure, heart rate, respiratory rate), procedures, meds, resuscitation requirements (crystalloid, blood or blood component), adjuncts including tranexamic acid, factor VII, PCC, fibrinogen, ED disposition.

OR Data: Procedures, operations, resuscitation requirements (crystalloid, blood or blood component), type of anesthesia, vasopressor requirement, adjuncts including tranexamic acid, factor VII, PCC, fibrinogen, disposition, serial vitals (blood pressure, heart rate), OR disposition, core temperature.

Resuscitation Data: Whole blood resuscitation, time of transfusion, WB characteristics (titer, blood type, matched/unmatched, leukocyte reduced, platelet sparing), component blood resuscitation, time of transfusion, transfusion ratios, adjuncts including tranexamic acid, factor VII, PCC, fibrinogen.

Linking Investigations in Trauma and Emergency Services

Task Order 2: Shock, Whole blood and Assessment of TBI (SWAT)

Outcome Data: 4 hour, 6 hour and 24 hour mortality, MOF score (7days), nosocomial infection, acute hemolytic transfusion reaction, cause of mortality, time to hemostasis, venous thromboembolism (VTE).

TBI Data: Serial GCS, TBI severity (AIS codes), TBI classification (subarachnoid, subdural, intracerebral hemorrhage, epidural, +/- shift, multifocal with specific classification) TBI progression, ICP data, operative intervention, paralysis, benzodiazepine coma, hypertonic resuscitation, GOAT and GOSE at discharge and 6 months respectively.

Eligible patients for the prospective cohort study will have de-identified data configured for compilation into the web based data entry platform with appropriate and all security measures in conjunction the DCC.

Mechanistic Banked Samples: Samples within the 0 hour (+ up to 2 hours), at 4 hours (+/- 2 hours) and 24 hours (+/- 12 hours) will collected and stored for analyses. We will perform batched sample analyses of enrolled patient subgroups +/- coagulopathy and +/- TBI across the receipt of WB vs. component therapy. We will measure markers of endothelial cell injury including Syndecan-1 and Hyaluronan, markers of neurological injury and neuron cell death including S100B protein and Neuron Specific Enolase (NSE), and end points of coagulopathy including Thrombin-antithrombin complex (TAT), activated Protein C (aPC), tissue Plasminogen Activator (tPA) and Plasminogen Activator Inhibitor (PAI-1).

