Sample Tracking, Management and Storage: After sample obtainment, processing and storage, samples will initially be batched sent to the University of Pittsburgh biological sample repository where it will be tracked, managed and stored until the necessary translational or mechanistic measurement are performed. The CCC and DCC have a long track record of coordinating such processes.

Power Analysis: The prospective cohort study will utilize time to 4 hour mortality for its primary outcome to power the study. Based upon the 6 LITES Network sites admission history that will be utilized and their respective volume of hemorrhagic shock patients meeting inclusion and exclusion criteria and a 3.5 year enrollment time period, we plan to initiate sampling on 1,050 patients over the enrollment time period of the study. With an 85% consent rate which is an estimate based upon prior studies of similar nature, we will consent for participation 892 patients for the study. With an estimate baseline rate of 4 hour mortality of 11.1 % derived from the PROPPR study, there will be 90% power to detect a hazard ratio of 1.9.

Calculations are based on the primary aim of the study based on the following assumptions:

- Type I error rate of 0.05
- Two-sided alternative hypothesis

Linking Investigations in Trauma and Emergency Services

Task Order 2: Shock, Whole blood and Assessment of TBI (SWAT)

- 6 sites will be involved, three whole blood and three component sites
- Each site will enroll 175 participants in 3.5 years of enrollment, of which, 85% will be eligible for the study (149)
- The calculations are based on Cox proportional hazard model
- A 4 hour event rate in the control (non-whole blood) group of 0.111

The power calculations for these secondary aims are presented below. When reporting the results of the analyses, caution will need to be taken with respect to the interpretation of the findings since they are secondary in nature.

The secondary outcomes in Aim 1B include binary outcome, continuous outcomes, and time to event outcomes. For the binary outcomes, the odds ratio that can be detected is presented in Table 1. For the continuous outcome, the effect size that can be detected is 0.13. Finally, for the time to event outcomes, the hazard ratio that can be detected over a range of event rates in the control group is also presented in Table 1.

Event Rate	.1	.2	.3	.4	.5	.6
Odds Ratio	1.76	1.56	1.49	1.46	1.46	1.48
Hazard Rate	2.69	1.70	.37	.30	.27	.30

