- For Aim 1C, a nonparametric analysis of variance will be used to compare the distribution of the GOS-E between the two groups. An effect size of 0.17 could be detected.
- For aim 2A, a nonparametric analysis of variance will be used to compare the distribution of the GOS-E between the two groups. An effect size of 0.28 could be detected.
- For aim 2B, a nonparametric correlation coefficient will be used to assess the association between GOS-E and the area under the systolic blood pressure curve. For each, a 95% confidence interval with a width of 0.19 can be estimated.
- For all secondary analyses, the type I error rate was set to 0.05, with a two-sided alternative hypothesis, and 90% power. For the Aim 1, the sample size will be 1,190. For Aim 2, the sample size will be limited to those with a traumatic brain injury. For the purposes of this study, this is expected to be 35% or a total of 417 participants.

Analyses

AIM#1: The analysis will begin by describing the baseline demographic and clinical characteristics of the overall population and then stratified by whole blood usage. The characteristics will be

Linking Investigations in Trauma and Emergency Services

Task Order 2: Shock, Whole blood and Assessment of TBI (SWAT)

compared among those who receive and who do not receive whole blood. For discrete variables, proportions will be generated and a chi-square test will be used to test for differences between the proportions. For continuous characteristics, means (medians) and standard deviations (interquartile ranges) will be calculated and t-tests (Wilcoxon) will be used to compare the means (distributions) among those who receive and do not receive whole blood.

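### The discharge analysis of Hypotheses 2A and 2B names no outcome and no cut, and its apparently two-level logistic model would force the graded discharge scores (GOAT, GCS) to be dichotomised

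*Combined protocol and SAP*

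**What the plan says.** Hypotheses 2A and 2B each make a claim at discharge as well as at 6 months. At 6 months the outcome is GOS-E, analysed with a hierarchical polytomous logistic model. For discharge, the Hypothesis#2A and Hypothesis#2B paragraphs under Analyses, AIM#2 both end with one sentence: "The same analytic approach will be used to measure outcomes at discharge except a hierarchical logistic regression model will be used". Neither paragraph names a discharge outcome, uses the word binary or gives a threshold.

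Other sections show which TBI measures belong to discharge:

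- Data Collection, TBI Data pairs the two scales with the two time points: "GOAT and GOSE at discharge and 6 months respectively". Table 1 also schedules GOAT at discharge.
- TBI Specific Outcomes lists GOAT at discharge and a discharge Glasgow Coma Scale score.
- Figure 4 scores GOAT as 100 minus total error, possibly negative, with three bands (76–100, 66–75, below 66). The GOAT definition says "Cutoff scores are available to identify abnormal, borderline, and normal orientation" and uses the test to judge capacity to consent. It does not link a band to the Hypothesis 2A or 2B analysis.

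The Power Analysis gives Aim 2 figures for 6-month GOS-E only: "An effect size of 0.28 could be detected" for 2A and "a 95% confidence interval with a width of 0.19 can be estimated" for 2B. No power is stated for any discharge outcome.

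**The concern.** The word *except* has a purpose only if the discharge model differs from the polytomous one, and the obvious difference is two outcome levels instead of several. A score that runs up to 100, or a GCS, can enter a two-level model only after being cut.

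Two things are then at stake. Differences among patients on the same side of the cut no longer count, so a real association between blood pressure and neurological status at discharge is easier to miss. And since no cut is prespecified and the GOAT has three bands rather than two, at least two cuts (normal against the rest, impaired against the rest) would be open once the data are in hand.

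The plan does not treat graded outcomes this way elsewhere. Continuous secondary outcomes under Hypothesis#1B stay on their own scale, and the Aim 2 power statements use methods for the whole distribution.

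**Working it through.** **1. What the text establishes.** In the Analyses section, multi-category models are called polytomous, while unqualified logistic models are fitted to yes/no variables (the boosted models for whole blood use and for SBP of 120 or more). This supports the two-level reading but does not prove it: Subgroup Analysis refers to a hierarchical logistic model for the primary outcome, although Hypothesis#1A specifies Cox. That GOAT or GCS is the discharge outcome is likewise an inference.

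**2. The plan's own Aim 2 figures.** Inputs from the Power Analysis: "For all secondary analyses, the type I error rate was set to 0.05, with a two-sided alternative hypothesis, and 90% power"; "this is expected to be 35% or a total of 417 participants"; "we will consent for participation 892 patients for the study".

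- TBI sample: 0.35 × 1,190 = 416.5, so 417 reproduces. Using 892 instead, 0.35 × 892 = 312.
- 2B interval width: 2 × 1.96/√(417 − 3) = 0.193, which matches 0.19.
- 2A effect size, assuming an even split and a standardised mean difference: 2 × (1.960 + 1.282)/√417 = 0.317, or 0.317/√0.955 = 0.325 for the Wilcoxon test. A value of 0.28 would need 2 × (3.242/0.28)² = 268.1, that is 269 per group or 538 patients. So 0.28 does not reproduce at 90% power. At N = 417 it corresponds to about 80%.

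The plan does not say what metric 0.28 is in. It is used below only as an assumed standardised shift, borrowed from 6-month GOS-E.

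**3. Illustration for 2A: N = 417, even split, normal score, shift 0.28.**

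- Full score: 0.28 × √(417/4) = 2.859; power = Φ(2.859 − 1.960) = 81.6%. For Wilcoxon: 2.859 × √0.955 = 2.794; power = Φ(0.834) = 79.8%.
- Median cut: proportions 0.500 and Φ(0.28) = 0.610, difference 0.110; pooled standard error 0.0487, unpooled 0.0484; power = Φ((0.1103 − 1.960 × 0.0487)/0.0484) = 62.1%.
- Difference: 79.8 − 62.1 = 17.7 points (Wilcoxon), or 81.6 − 62.1 = 19.5 points.

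**4. Varying the assumptions.** Simulation with 4,000 trials per setting and shift 0.28. The full score is tested by rank-sum and the normal/not-normal cut by a z-test of proportions. Shares normal and at the ceiling refer to the unexposed and are assumed.

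| N | Exposed | Normal | At ceiling | Full score | Cut | Gain (points) |
|---|---|---|---|---|---|---|
| 417 | 50% | 50% | 0% | 80% | 62% | 18 |
| 417 | 50% | 60% | 20% | 78% | 60% | 18 |
| 417 | 50% | 70% | 30% | 77% | 56% | 21 |
| 417 | 50% | 70% | 50% | 69% | 54% | 15 |
| 312 | 50% | 60% | 20% | 66% | 49% | 17 |
| 312 | 50% | 70% | 30% | 64% | 43% | 21 |
| 220 (assumed scorable) | 50% | 60% | 20% | 51% | 36% | 15 |
| 417 | 25% | 60% | 20% | 66% | 47% | 19 |

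Less favourable settings:

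- 10% exposed, 60% normal, 20% at ceiling: about 13, 9 and 7 points at N = 417, 312 and 220. Over other distributions with 10% exposed, about 4 to 14.
- Even split, 80% normal, 70% at ceiling: about 7 to 12 points as N goes from 220 to 417.
- 30% tied at the worst rank (deaths, untestable): roughly 10 to 15 points.

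Each simulated power has a standard error of at most √(0.25/4,000) = 0.8 points, so gains repeat only to within about two points. Using the three bands instead of two recovers only 1 to 4 points in the main settings.

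Site clustering and propensity adjustment are left out of both analyses. For 2B the exposure is a continuous pressure area analysed in five propensity strata, so these two-group figures do not carry over.

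**The case against.** The strongest reply is that the plan never says GOAT or GCS will be cut in two. The hypotheses speak only of TBI or neurological outcomes at discharge. Survival at discharge is scheduled in Table 1, discharge disposition is recorded, and the TBI list contains several yes/no items such as craniotomy and ICP monitoring. If one of the binary items is meant, logistic regression is right and nothing is lost. This stands: a reader might infer that dichotomising is the stated plan, but the documents support only the narrower point that the outcome and cut are undefined and that a two-level model does not fit the graded scores tied to discharge.

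A reader might also infer a fixed loss, such as a firm 15 to 20 points. The documents do not support that either. They give no score distribution, ceiling, exposure split or discharge effect size. Hypothesis 2A concerns a nadir SBP of at least 120, while SBP of 90 or below is one of the entry criteria, and everyone who enters by it falls in the lower group. An even split may therefore be optimistic, and the gain shrinks as the exposed group does. A coarse score cut at its best point can lose as little as about 2 points, and a poorly placed cut can lose more than 30.

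Two further objections are fair. GOAT is given orally, so it has no value for patients who die or cannot be tested, and an ordinal model needs a rule for them. And discharge is a lesser part of a secondary aim: 6-month GOS-E is the principal TBI outcome, and the Power Analysis already advises caution with secondary findings.

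**Conclusion.** The point holds as an undefined outcome and cut, combined with a model that on its natural reading would discard information from the graded discharge scores. It does not hold as a documented decision to dichotomise, as a fixed loss of power, or as a demonstrated shortfall in a powered analysis, since no discharge power was claimed.

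For 2A, the illustrative gain from using the full score is about 18 points in the base case and about 4 to 21 points over the settings tried. It is smallest when few patients reach the nadir threshold or most sit at the ceiling. It rests on the borrowed shift of 0.28 and on assumed distributions, and the range is not a bound. For 2B the direction is the same but no size is established. This is a cheap improvement to a secondary analysis.

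**What to change.** In the Hypothesis#2A and Hypothesis#2B paragraphs under Analyses, AIM#2:

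- Name the discharge outcome: the GOAT total, with discharge GCS as a second score.
- Replace the logistic model for these scores with a hierarchical ordinal (cumulative-logit) model. Keep the same propensity term (2A) or propensity strata (2B) and the same site effect, and estimate one common log odds ratio for SBP of at least 120 (2A) or for the pressure area (2B).
- Prespecify how sparse score values are grouped, and place deaths and patients untestable because of their injury in stated worst categories.
- Report the three GOAT bands descriptively only.
- Keep binary logistic regression for discharge outcomes that are truly binary, such as survival, and name them.

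The cost is SAP wording and one model change. No new data should be needed, because both scores are listed for collection. Table 1 shows GCS only up to 24 hours, however, so confirm that the discharge GCS listed under TBI Specific Outcomes is recorded. The downside is a proportional-odds assumption, which should be examined, and an effect measure slightly less intuitive than a proportion with normal orientation. The descriptive bands cover that second point.
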